8.4.8.1 Anaphylaxis/Hypersensitivity Events

The following anaphylaxis/hypersensitivity events ([Table 4](#)) are defined as AESI in this study. The Sponsor will provide each site with an AESI guidance document (or equivalent). Refer to the AESI guidance document (or equivalent) for the most updated list of terms, definitions, and additional details.

Table 4 Terms for Anaphylaxis/Hypersensitivity Events

Term	Definition
Anaphylaxis	A disorder characterized by an acute inflammatory reaction resulting from the release of histamine and histamine-like substances from mast cells, causing a hypersensitivity immune response. Clinically, it presents with breathing difficulty, dizziness, hypotension, cyanosis, and loss of consciousness and may lead to death.
Angioedema	Localized, non-pitting, and transient swelling of submucosal or subcutaneous region.
Bronchospasm	A disorder characterized by a sudden contraction of the smooth muscles of the bronchial wall.
Drug hypersensitivity (drug-related allergic reaction)	Adverse effects of drugs that clinically resemble allergic reactions. Immediate clinical manifestations may include urticaria, angioedema, rhinitis, conjunctivitis bronchospasm, and anaphylaxis. Delayed clinical manifestations may include urticaria, maculopapular eruptions, fixed drug eruptions, vasculitis, toxic epidermal necrolysis (TEN), Stevens-Johnson syndrome (SJS), drug reaction with eosinophilia and systemic symptoms (DRESS), and acute generalized exanthematous pustulosis (AGEP).
Dyspnea (difficulty breathing)	A disorder characterized by an uncomfortable sensation of difficulty breathing.
Hypersensitivity	Excessive immune response. Clinically, manifestations may include allergic manifestations such as urticaria, anaphylaxis, angioedema, allergic rhinitis, Stevens-Johnson syndrome (SJS), toxic epidermal necrolysis (TEN), acute generalized exanthematous pustulosis (AGEP), drug reaction with eosinophilia and systemic symptoms (DRESS), serum sickness, and vasculitis.
Dysphonia	A disorder characterized by an inflammation involving the larynx.
Wheezing	A disorder characterized by a high-pitched, whistling sound during breathing. It results from the narrowing or obstruction of the respiratory airways.

Before study start, the investigator or medically qualified designee will receive support from the Sponsor to assist in identifying the anaphylaxis/hypersensitivity AESI terms listed above in addition to instructions on the process from identification to data entry. At the RSV Season 1 Day 1 visit, the investigator will provide anticipatory guidance to the legally acceptable representative for a suspected anaphylaxis or hypersensitivity event.

If any anaphylaxis/hypersensitivity event is reported in the eDiary or during weekly surveillance contact (through 14 days post Dose 2 in RSV Season 1, within 42 days postdose in RSV Season 2, or within 42 days after an additional post-surgery dose of MK-1654 in either RSV season), further assessment by the site may be required. The site must call the legally acceptable representative for additional information; if it is determined that an onsite assessment is required, a site visit should be conducted as soon as possible after becoming aware of the anaphylaxis/hypersensitivity event or within 3 days.

In addition, the legally acceptable representative should call the site as soon as possible if they suspect an anaphylaxis/hypersensitivity event or within 3 days of event onset.

In the event a participant experiences a Grade 3 or 4 anaphylaxis/hypersensitivity AESI postdose, as confirmed by the investigator, an additional blood draw is required for evaluation for potential ADA to MK-1654, and additional ADA characterization if indicated (see Section 1.3 and Section 10.2 [Appendix 2]).

8.4.8.2 Rash Events

The following rash events ([Table 5](#)) are defined as AESI in this study. Refer to the AESI guidance document (or equivalent) for the most updated list of terms, definitions, and additional details.

Table 5 Terms for Rash Events

Term	Definition
Acute generalized exanthematous pustulosis (AGEP)	A disorder characterized by fever and sterile pustules, circumscribed and elevated skin lesions filled with pus.
Drug eruption	An adverse skin reaction to a drug, not otherwise included in this table of rash terms.
Drug reaction with eosinophilia and systemic symptoms (DRESS)	A disorder characterized by fever, influenza-like symptoms, skin rash, eosinophilia, with or without atypical lymphocytes, elevated transaminase concentration, and/or impaired renal function.
Erythema multiforme	A disorder characterized by target lesions (a pink-red ring around a pale center).
Generalized rash of exfoliative nature (including dermatitis exfoliative and exfoliative rash)	A disorder characterized by generalized inflammatory erythema and exfoliation. The inflammatory process involves >90% of the body surface area.
Stevens-Johnson syndrome (SJS)	A disorder characterized by $\leq 30\%$ total body skin area separation of dermis. The syndrome is thought to be a hypersensitivity complex affecting the skin and the mucous membranes.
Toxic epidermal necrolysis (TEN)	A disorder characterized by $>30\%$ total body skin area separation of dermis. The syndrome is thought to be a hypersensitivity complex affecting the skin and the mucous membranes.
Urticaria	A disorder characterized by an itchy skin eruption characterized by wheals with pale interiors and well-defined red margins.

The investigator or medically qualified designee will receive support from the Sponsor to assist in identifying the rash AESI terms listed above (eg, representative photographic images) in addition to detailed instructions on the process from identification to photographic image submission. At the RSV Season 1 Day 1 visit, the investigator will provide anticipatory guidance to the legally acceptable representative for suspected rash events.

If any rash event is reported in the eDiary or during weekly surveillance contact (Day 1 through 14 days post Dose 2 in RSV Season 1, within 42 days postdose in RSV Season 2, or within 42 days after an additional post-surgery dose of MK-1654 in either RSV season), further assessment for AESI by the site may be required. The site must call the legally acceptable representative for additional information; if it is determined that an onsite assessment for AESI is required, a site visit should be conducted as soon as possible after becoming aware of the rash event or within 3 days. Photographs (see Section 8.4.8.2.1) and a dermatology consultation (see Section 8.4.8.2.2) may also be required.

In addition, the legally acceptable representative should call the site as soon as possible if they suspect a rash AESI or within 3 days of event onset.

8.4.8.2.1 Photography

If a participant has a suspected or confirmed rash AESI on evaluation, photographs must be taken. For all other rashes (non-AESI), photographs are not required.

Photographs will be taken to document the visual appearance and scope of dermal involvement. Whenever possible, photographs of participant's faces or any other identifying features should be avoided or redacted. Sites should follow local policies for maintaining participant confidentiality and privacy.

Before the end of the visit, the photographs should be reviewed by site staff to ensure they meet the imaging vendor requirements; additional photographs should be taken if needed. All photographs will be uploaded to the central vendor repository.

The imaging vendor will provide the following to each site:

- Training
- Details and requirements for the photographs (eg, number of photos, lighting)
- Instructions for uploading photographs to the vendor repository
- All imaging equipment

8.4.8.2.2 Dermatology Consultation

Severe rash AESI (Grade 3 and Grade 4) are unusual in general pediatric practice and therefore require evaluation by dermatologic specialists.

If the investigator determines that the suspected rash is indeed a Grade 3 or 4 AESI, every effort should be made to schedule a consultation with a local dermatologist (pediatric dermatologist is preferred where possible). This consultation with the local dermatologist should occur as soon as possible or within 3 days from the time the site diagnoses the Grade 3 or Grade 4 AESI.

The purpose of the dermatology consultation is to gain confirmation of the rash diagnosis. This consultation should be conducted per local standards of care. The dermatologist should be provided access to the photos taken at the site visit and copies of relevant source documents collected for the purpose of this study.

After the dermatology consultation, the local dermatologist's assessment and recommendations should be obtained. The diagnosis from the local dermatologist as well as any procedures or other intervention should be recorded on the appropriate eCRFs and added to the source documents.

See the AESI guidance document (or equivalent) for additional details.

8.5 Treatment of Overdose

In this study, an overdose is any dose higher than the protocol-defined dose.

No specific information is available on the treatment of overdose.

8.6 Pharmacokinetics

The decision as to which serum samples collected will be tested to evaluate PK will be determined by the Sponsor. If indicated, these samples may also be tested and/or pooled for testing in an exploratory manner for metabolites and/or additional markers.

See the Pharmacokinetics/Immunogenicity/Pharmacodynamics schedule in the SoA for the timing of each blood draw. Detailed instructions including blood volumes to be drawn are provided in the laboratory manual.

8.7 Immunogenicity

8.7.1 Blood Collection for Antidrug Antibodies (ADA) Assay

Sample collection, storage, and shipment instructions for serum samples are provided in the laboratory manual. See the Pharmacokinetics/Immunogenicity/Pharmacodynamics schedule in the SoA for the timing of each blood draw.

8.8 Pharmacodynamics

8.8.1 Blood Collection for Serum Neutralizing Antibodies Against RSV (SNA) Assay

Sample collection, storage, and shipment instructions for pharmacodynamic samples are provided in the laboratory manual. See the Pharmacokinetics/Immunogenicity/Pharmacodynamics schedule in the SoA for the timing of each blood draw.

8.9 Gene Sequencing and Sensitivity Testing

8.9.1 Nasopharyngeal Sample Collection for RT-PCR Testing and RSV F Gene Sequencing for Sensitivity to MK-1654

See the SoA (Section 1.3) and Section 8.2.3 for the timing of collection of the NP sample for RT-PCR testing for respiratory virus identification.

RSV F gene sequencing will only be performed if the NP specimen tests positive for RSV.

Detailed instructions are provided in the laboratory manual.

8.10 Biomarkers

Biomarkers are not evaluated in this study.

8.11 Future Biomedical Research Sample Collection

If the participant's legally acceptable representative provides documented informed consent for FBR, the following specimens will be obtained as part of FBR:

- DNA for future research.
- Leftover serum from the PK assay will be stored for future research.
- Leftover serum from the ADA, SNA, and additional ADA characterization assays will be stored for future research.
- Leftover NP swabs from RT-PCR testing will be stored for future research.

8.12 Medical Resource Utilization and Health Economics

Medical Resource Utilization and Health Economics are not evaluated in this study.

8.13 Visit Requirements

Visit requirements are outlined in Section 1.3. Specific procedure-related details are provided in Section 8.1 through Section 8.11. Additional specific requirements are detailed below.

8.13.1 Screening (RSV Season 1 Day 1 Visit Predose)

At the RSV Season 1 Day 1 visit, potential participants will be evaluated to determine whether they meet entry requirements as set forth in Section 5. Potential participants will be screened at the study site. Participants who have the following are not eligible for enrollment, but may be rescreened:

- Recent illness with fever (rectal temperature $\geq 100.5^{\circ}\text{F}$ [$\geq 38.1^{\circ}\text{C}$] or axillary temperature $\geq 100.0^{\circ}\text{F}$ [$\geq 37.8^{\circ}\text{C}$]) within 72 hours predose (see Section 5.2 Exclusion Criteria #12) (See Appendix 7.2 for specific requirements for participants in the Czech Republic.)
- LRI symptoms (defined in Section 8.2.1) within 7 days predose (see Section 5.2 Exclusion Criteria #13)

Participants may be rescreened up to 4 times. Screening procedures listed in the SoA (including consent review; see Section 1.3.1) should be repeated at each rescreen visit.

8.13.1.1 Predose Nasopharyngeal Sample Collection for RT-PCR Testing

If symptoms of ARI listed in Section 8.2.1 have been present within 7 days before the RSV Season 1 Day 1 visit, an NP sample should be collected. Collecting an NP sample at this visit

does not exclude an infant from participating in the study. See Section 8.13.1 if symptoms of LRI are present within 7 days predose.

8.13.2 Randomization/Dose Administration/Observation

If a participant is deemed eligible for the study, and completes all other predose procedures, the participant will be assigned a unique treatment/randomization number by the IRT system.

Predose samples should be collected from randomized participants only. Samples should be collected after randomization in the IRT system but before dose administration. If the predose blood sample cannot be collected after 3 attempts, the dose should be administered.

After randomization in the IRT system, participants will receive study intervention administered as a single dose via IM injection at the study site as described in Section 6.1 and Section 8.

Participants will be observed at the study site for at least 30 minutes after each dose for any immediate AEs (see Section 8.3.4). (See Appendix 7.2 for specific postdose observation requirements for participants in the Czech Republic.) This observation must be performed by the blinded investigator and/or study staff for Doses 1 and 2 in RSV Season 1.

Vital sign measurements should be repeated at the end of the 30-minute postdose safety observation period.

8.13.3 Delay in Randomization and Study Medication Administration

All efforts should be made to randomize participants and administer study medication on RSV Season 1 Day 1 after predose screening procedures as per protocol. However, if randomization and study medication administration cannot be conducted on Day 1, they may be conducted within 5 days of the predose screening procedures (RSV Season 1 Day 1).

Prior to randomization in the IRT system and administration of study medication, the site should confirm participant's eligibility by repeating vital signs measurements, the full physical examination (including weight), and review the eligibility criteria and the informed consent.

8.13.4 Early Withdrawal Visit

If the legally acceptable representative withdraws consent prior to the last scheduled study visit, the participant should be brought in for an unscheduled visit (at the study site, at home, or at an alternate study site location; see Section 8.13.5). The unscheduled visit should follow the applicable Day 150 visit procedures based on the participant's treatment assignment and the current RSV Season (1 or 2).

If the participant withdraws consent while attending a scheduled visit, any additional assessments and procedures needed for the participant's respective final study visit should be conducted in addition to the assessments and procedures for the scheduled visit.

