1.3.1 RSV Season 1 Schedule of Activities

1.3.1.1 Schedule of Activities RSV Season 1 Day 1 Up to Day 60 Visit (All Participants; Part 1 – Double-blind)

Study Period	Screening, Randomization, and Intervention			Follow-up RSV Season 1 (Day 1 Up to Day 60 Visit)							Notes
Visit Number/Title	1			TC	2	Weekly contact start	3	TC	4A	UNSCH	See Section 8.13 for descriptions of study visits. UNSCH for respiratory infection and AESI assessment and early withdrawal, if indicated.
RSV Season 1 All Participants Part 1 Scheduled Day and Window (Days):	Day 1			3 (-1) ^a	7 (+2)	14 (±2 ^b)	28 (+4)	42 (+4) ^c	60 ^d (see Section 1.3.1.2 and Section 1.3.1.3)	If indicated	^a If Day 3 is not a business day, the phone call should occur on Day 2. ^b ±2-day window applies to all weekly contacts. ^c At least 14 days after Dose 2. ^d Participant’s treatment assignment will be unblinded at the Day 60 visit (28-32 days after Dose 2).
	Predose	Dose	Post-dose								
Administrative Procedures											
Informed Consent	X										Participants consented for 1 or 2 RSV seasons depending on eligibility (see Section 5.1 and Section 5.2).
Informed Consent for FBR	X										Participation in FBR is optional and consent must be obtained before collection of buccal swab DNA samples.
Inclusion/Exclusion Criteria	X										
Participant Identification Card	X										Randomization number will be added to the card.
Medical History	X										
Prior/Concomitant Medication Review	X		X	X	X	X	X	X		X	Concomitant medications will be collected from Day 1 to 14 days after Dose 2, afterwards only concomitant medications associated with an AE/SAE will be recorded.
Predose NP Sample Collection for RT-PCR Testing	X (if indicated)										Collect if respiratory infection symptoms are present within 7 days before the Day 1 visit. See Section 8.13.1.1 and Section 8.2.3.
Assignment of Randomization Number	X										

Study Period	Screening, Randomization, and Intervention			Follow-up RSV Season 1 (Day 1 Up to Day 60 Visit)						Notes	
Visit Number/Title	1			TC	2	Weekly contact start	3	TC	4A	UNSCH	See Section 8.13 for descriptions of study visits. UNSCH for respiratory infection and AESI assessment and early withdrawal, if indicated.

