All study participants will receive 2 blinded doses before unblinding in RSV Season 1:

- MK-1654 group: MK-1654 (Dose 1) and placebo (Dose 2)
- Palivizumab group: palivizumab (Dose 1 and Dose 2)

All participants, irrespective of treatment group, will have safety monitoring (AEs and SAEs), efficacy surveillance to monitor the incidence of RSV-associated MALRI and hospitalization, and blood sample collection as described in the SoA (see Section 1.3.1.1 SoA – RSV Season 1 Part 1).

Participant's treatment assignment will be unblinded at the Day 60 visit before any visit procedures. Participants in the MK-1654 group do not have any additional planned doses in RSV Season 1 and will continue with safety monitoring, efficacy surveillance, and blood sample collection as described in the SoA (see Section 1.3.1.2 SoA – RSV Season 1 Part 2 – MK-1654 Group). Participants in the palivizumab group will receive at least 3 and up to 5 single doses of palivizumab, once every 28 (+4) days (inclusive of dosing day; minimum of 28 days between doses), depending on the timing of enrollment relative to the RSV season. For calculating the visit windows for subsequent administrations, the day of the previous administration is considered Day 1. These participants will continue with safety monitoring and efficacy surveillance as described in the SoA (see Section 1.3.1.3 SoA – RSV Season 1 Part 2 – Palivizumab Group).

For infants enrolled and consented to participate in RSV Seasons 1 and 2, inclusion/exclusion criteria will be rechecked at the Day 240 visit for eligibility to continue in RSV Season 2 (see Section 5.1 and Section 5.2). Participants still eligible will begin the RSV Season 2 between 246 to 393 days after RSV Season 1 Dose 1, depending on the timing of enrollment relative to the RSV season (see Section 8.1.8.1). Participants in the palivizumab group who are continuing in RSV Season 2 will have blood sample collection at the Day 240 visit to serve as the baseline for RSV Season 2. All participants not continuing in RSV Season 2 will be monitored for safety for 365 days after receiving the first dose in RSV Season 1.

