4.2 Scientific Rationale for Study Design

This study will evaluate the safety and tolerability of MK-1654 versus palivizumab and collect efficacy data to estimate the efficacy of MK-1654 relative to palivizumab in this population at increased risk for severe RSV, in accordance with the 2017 draft FDA Guidance for Industry: *Respiratory Syncytial Virus Infection: Developing Antiviral Drugs for Prophylaxis and Treatment* [Food and Drug Administration 2017].

This study will also assess the PK of MK-1654 at various time points up to 240 days after the first dose to observationally compare the PK data in this population to the PK of MK-1654 determined in the Phase 2b/3 pivotal efficacy study (MK-1654-004 [PN004] in healthy pre-term and full-term infants). In addition, MK-1654 PK will be assessed for up to 150 days after the RSV Season 2 dose.

Since the PK of palivizumab has been well studied and described in the literature, blood samples will not be collected from infants who are enrolled for 1 RSV season in the palivizumab group after the participant's treatment assignment is unblinded at the Day 60 visit in RSV Season 1. These eligible participants in the palivizumab group who will receive MK-1654 in RSV Season 2 will have PK, ADA, and SNA blood samples collected according to the SoA (see Section 1.3.1.3 SoA – RSV Season 1 Part 2 – Palivizumab Group).

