6.3.3 Blinding

In Part 1 of this study (up to the Day 60 visit), a double-blinding technique will be used. MK-1654, palivizumab, and placebo will be prepared and administered in a blinded fashion by an unblinded pharmacist or medically qualified study personnel not otherwise involved in the conduct of the study. Unblinded study personnel should not have contact with participants for any study-related procedures/assessments postdose (prior to unblinding), including all safety follow-up procedures. The participant's legally acceptable representative,

the investigator(s), and Sponsor personnel or delegate(s) will be unaware of the study intervention assignments.

Part 2 of this study (time of unblinding through duration of participation in the study) is conducted as open-label therefore, the Sponsor, investigator, and participant/participant's legally acceptable representative will know the intervention administered.

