8.1.9 Discontinuation and Withdrawal

Participants who discontinue study intervention prior to completion of the treatment period should be encouraged to continue to be followed for all remaining study visits as outlined in Section 1.3.

Participants who withdraw from the study should be encouraged to complete all applicable activities scheduled for the final study visit at the time of withdrawal. Any AEs that are present at the time of withdrawal should be followed in accordance with the safety requirements outlined in Section 8.4.

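### The early-withdrawal rule picks procedures by treatment arm with no exception for the blinded period, so following it before Day 60 discloses the allocation to site staff

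*Combined protocol and SAP*

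**What the plan says.** The first paragraph of Section 8.13.4 applies when the representative withdraws consent before the last scheduled visit. The infant should be brought in, and "The unscheduled visit should follow the applicable Day 150 visit procedures based on the participant's treatment assignment" and the current RSV season. No separate instruction is given for Part 1.

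Early withdrawal during Part 1 is foreseen. The schedule for the double-blind period has an unscheduled-visit column, described as "UNSCH for respiratory infection and AESI assessment and early withdrawal, if indicated". That column marks no routine PK, ADA or SNA sample, only an ADA sample after a Grade 3 or 4 anaphylaxis/hypersensitivity event.

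On blinding, Section 6.3.3 states: "In Part 1 of this study (up to the Day 60 visit), a double-blinding technique will be used". During that time the representative, "the investigator(s), and Sponsor personnel or delegate(s) will be unaware of the study intervention assignments". Section 4.1 sets the planned end of the blind: "Participant's treatment assignment will be unblinded at the Day 60 visit before any visit procedures". Section 8.1.10 permits unmasking only where the infant's welfare requires it.

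Two other instructions bear on withdrawal. Section 8.1.9 says that withdrawing participants "should be encouraged to complete all applicable activities scheduled for the final study visit at the time of withdrawal". The second paragraph of Section 8.13.4, for withdrawal during a scheduled visit, likewise points to the final study visit and not to Day 150.

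**The concern.** A rule that selects procedures by arm is harmless once the arm is known. Before Day 60 it asks a blinded team to act on information that it is not supposed to have. If the arm-specific procedure is visible, carrying it out gives the information away.

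The stake is the blinded safety comparison. The primary endpoints are comparative safety, and Section 9.6.2 makes the period after the first two doses the primary comparison. Section 4.2.3 gives unbiased assessment over the 42 days after Dose 1 as the reason for the placebo injection. AE severity and causality are investigator judgements, and AE/SAE review is part of the withdrawal visit. Nothing in Section 8.13.4 requires those judgements to be recorded before the arm-dependent step.

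**Working it through.** No sample size or error rate is at issue, so the check is a comparison of schedules, with some arithmetic on blood volumes.

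**Step 1. Compare the Day 150 column (Visit 5) of the two Season 1 Part 2 schedules.**

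| Day 150 item | MK-1654 (Section 1.3.1.2) | Palivizumab (Section 1.3.1.3) |
|---|---|---|
| Medication review, brief examination with weight and length, vital signs, AE/SAE review | yes | yes |
| Weekly surveillance; respiratory assessment and NP sample if indicated | yes | yes |
| PK, ADA and SNA blood | yes | no (Day 240 only, if continuing to Season 2) |

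Palivizumab dosing and the 30-minute observation belong to Visits 4A to 4C, and eDiary review to those visits and the calls after them. None is marked at Visit 5. The three blood rows are the only difference.

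**Step 2. Check against Table 10 (Season 1 maximum volumes: Day 1, Day 7, Day 150, Day 240).**
- MK-1654: 2.4 + 1.0 + 2.4 + 2.4 = 8.2 mL, as stated.
- Palivizumab, one season: 2.4 + 1.0 = 3.4 mL, as stated.
- Palivizumab, two seasons: 2.4 + 1.0 + 2.4 (Day 240) = 5.8 mL, as stated.

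The totals reproduce only with no Day 150 draw for palivizumab. Choosing the Day 150 list by assignment therefore means deciding whether to draw blood.

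**Step 3. Ask who could carry this out before Day 60.** The investigator and site team are blinded. Section 6.3.3 bars unblinded personnel from postdose study procedures until unblinding. If the IRT system or the unblinded pharmacist relays only whether to draw, that instruction identifies the arm to anyone who knows the two schedules. Withdrawal of consent is not a welfare reason under Section 8.1.10.

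**Step 4. Bound the affected group.** Only Season 1 withdrawals before the Day 60 unblinding are concerned. Later Season 1 follow-up is open-label. Season 2 is open-label with one schedule for all.

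**Step 5. Check that a uniform draw would fit.** Section 8 allows about 0.8 mL/kg per visit and 2.4 mL/kg over four weeks. At 3 kg (the lower weight bound of Table 10) these are 2.4 mL and 7.2 mL. An infant withdrawn within four weeks of Day 1 would give at most 2.4 + 1.0 + 2.4 = 5.8 mL, or 7.0 mL with the 1.2 mL event-driven sample. In a lighter infant the per-visit cap holds three draws to 3 × 0.8 = 2.4 mL/kg. A fourth draw might have to be reduced or omitted, as is already true for MK-1654 infants under the present rule.

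**The case against.** The strongest reply is that this is a drafting gap and not an order to unblind. The arm-specific Day 150 lists exist only in schedules headed as open-label, so the rule can be read as presupposing a known assignment. Section 4.2 fits that reading: it says "blood samples will not be collected from infants who are enrolled for 1 RSV season in the palivizumab group after" the Day 60 unblinding, so it does not forbid sampling both arms alike before then. This has force, and nothing suggests that unblinding was intended. But the rule has no such limit, the Part 1 schedule expressly provides for early withdrawal, and a site following the text literally would break the blind.

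The limits on harm also stand:
- Section 9.2 calls for each participant's available safety data to be reviewed and locked before unblinding. It is written around the Day 60 visit, however, and Section 8.13.4 does not place the withdrawal visit after such a lock.
- AEs will already have been collected under blind through the eDiary, the Day 3 call, the Day 7 visit and weekly contacts.
- A withdrawn infant has no later scheduled assessments that could be biased.
- Families may decline the visit, loss to follow-up is handled separately in Section 7.3, and withdrawal during a scheduled visit falls under the second paragraph of Section 8.13.4.

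A reader might also see a conflict in the lack of a routine PK or SNA draw in the Part 1 unscheduled-visit column. The open-label Season 1 schedules lack it there too, so this is a general mismatch with Section 8.13.4 and not specific to blinding.

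**Conclusion.** The point stands as a wording defect that should be corrected. For an infant withdrawn under the first paragraph of Section 8.13.4 before the Day 60 unblinding, following the rule requires the allocation and discloses it to site staff, contrary to Sections 6.3.3 and 8.1.10. Disclosure to the family is less certain. What is exposed is limited to what is newly assessed at that last visit.

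The documents give no number of withdrawals before Day 60, and it may be small. Three stronger readings are not supported:
- A reader might take the 10% attrition in Section 9.9.1 and compute 1000 × 10% × 60/150 = 40 infants. That rate is an assumption for the per-protocol efficacy population, whose criteria in Section 9.5.1 also exclude for incomplete dosing, certain procedures and protocol deviations. Even spacing over 150 days is a further guess.
- A reader might conclude that every early withdrawal would be disclosed. The declined visits and other routes noted above rule that out.
- A reader might suppose that early withdrawers are enriched for AEs. The documents do not say so, and Section 7.1 keeps infants who stop study intervention in follow-up.

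The conclusion rests on reading the schedules and Table 10 as printed, and on site staff knowing both schedules.

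**What to change.** Split Section 8.13.4 at the Day 60 unblinding.

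- **Before unblinding:** one procedure list for both arms that does not depend on allocation. Handle blood identically: either no routine PK/ADA/SNA draw in either arm, or the same draw in both within the existing volume limits. State that allocation is not consulted for this visit and that AE severity and causality are recorded without it.
- **After unblinding:** keep the present arm-specific Day 150 list.

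Reconcile Section 8.1.9, the second paragraph of Section 8.13.4 and the unscheduled-visit column of the Part 1 schedule with the new text, including which contact counts as the final study visit. Amend Table 10 if the uniform draw is chosen.

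The cost is protocol wording, plus either a few early-withdrawal PK samples lost or one extra draw in a few palivizumab infants. The uniform approach is already used in this trial, since both arms are sampled on Day 1 and Day 7.
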